9.2.3 Analysis Methods

Tables showing n and percent of participants with treatment-emergent worst toxicity grades (for tests with defined toxicity grades) and treatment-emergent worst abnormalities (for tests without a defined toxicity grades) during treatment phase will be generated.

A shift table showing the number and percent of participants with different toxicities at baseline vs treatment phase will be presented for lab tests with defined toxicity grades.

Shift tables showing n and percent of participants with various levels of abnormalities for Troponin-I and -T during treatment phase versus baseline will be generated.

Two eDISH plots showing peak total bilirubin vs peak ALT (and separately for peak AST) measurements during the treatment phase will be generated. Peak values (using \log_{10} scale) on the plot will show the maximum values that occur post-baseline during treatment phase (not necessarily concurrent events). Points on the plot will be distinguished for the two treatment groups. Two reference lines at 2xULN for total bilirubin and at 3xULN for ALT/AST will be shown on the plots. These reference lines will divide the plot into 4 sections showing (1) Hyperbilirubinemia, (2) Hy's Law range, (3) Normal range, and (4) Temple's Corollary range.

A listing of participants with treatment-emergent toxicities/abnormalities will be provided. This listing will include all other timepoints for the corresponding participant/lab test.

A listing of participants with Grade 3 or higher toxicity laboratory values will be provided.

9.3 Vital signs

9.3.1 General

Temperature, pulse rate, respiratory rate, oxygen saturation and blood pressure may be measured once or multiple times during screening/baseline and every day during the treatment phase.

9.3.2 Data Handling Rules

Because of the participants' disease severity, the vital signs may be measured in any position (supine, standing, semi-recumbent, or sitting). For the analysis all measurements irrespective of the position during the assessment will be considered.

All non-missing measurements will be considered for finding the worst abnormalities on a given study day or during the treatment phase.

Vital Signs abnormalities will be determined according to the WHO grading scale boundaries as mentioned in Attachment 1.

For each participant, baseline abnormality will be based on the baseline value (see section 4.1 for the baseline definition). The worst abnormality is determined for the treatment phase. All measurements including all post-baseline scheduled and unscheduled measurements during treatment phase will be used to evaluate worst abnormality during the treatment phase.

An abnormality (based on normal ranges) will be considered treatment-emergent if it is worse than the baseline abnormality. If the baseline abnormality is missing, the abnormality is always considered as treatment-emergent. A shift from "abnormally low" at baseline to "abnormally high" post-baseline (or vice versa) is also considered treatment-emergent.

9.3.3 Analysis Methods

A table showing number and percentage of participants with treatment-emergent worst abnormality during the treatment phase will be generated.

Vital signs data for participants having at least one treatment-emergent abnormality during treatment phase will be listed.

9.4 Electrocardiogram (ECG)

9.4.1 General

ECG measurements (in supine position) for PR interval, QRS interval, Heart Rate (HR) and QTc intervals (using Bazett's correction formula and Fridericia's correction formula) during screening and treatment phases are recorded on the eCRF.

9.4.2 Definitions

Treatment-emergent Abnormalities

ECG abnormalities will be determined according to the boundaries defined in Attachment 2.

For each participant, baseline abnormality (i.e., assessments that are out of normal ranges) will be based on the baseline value (see section 4.1 for the baseline definition). An abnormality during treatment phase will be considered treatment-emergent if it is worse than the baseline abnormality. If the baseline abnormality is missing, the abnormality is always considered as treatment-emergent. A shift from “abnormally low” at baseline to “abnormally high” post-baseline (or vice versa) is also considered treatment-emergent.

9.4.3 Data Handling Conventions

Investigator reported ECG related values (irrespective of the participant’s position at ECG evaluation) on the eCRF will be used for analysis without any recalculation. If on a day the ECG is performed multiple times, then for descriptive statistics the mean of the non-missing post-dose ECG evaluations will be used as the value for each specific parameter and study day.

All measurements at scheduled and unscheduled visits during the treatment phase will be considered in determining worst case values during the treatment phase.

9.4.4 Analysis Methods

Number and percent of participants in different categories of worst (and if treatment emergent) ECG abnormalities during treatment phase will be tabulated. The ECG abnormalities based on the change from baseline QTc values will be tabulated. Tables to show the shift from baseline to maximum corrected QT interval (actual values and change from baseline values) during treatment phase will be provided. A table showing shift in frequencies of ECG Interpretations reporting ‘ST or T Waves, Ischemia or Infarction’ from baseline values (Yes, No, or missing) to post-base values (Yes, No, or missing) will be generated.

Listings of ECG values and Troponin I/T; of participants with Abnormal ST or T Wave, Ischemia, or Infarction; and with ECG abnormalities will be generated.

ATTACHMENTS

ATTACHMENT 1. WHO GRADING SCALE VITAL SIGNS

The following abnormalities are defined for vital signs:

| Vital Signs parameter | | | |
|-----------------------|-----------|------------------------|-------------------------|
| Abnormality Code | Pulse | DBP* | SBP* |
| Abnormally low | < 45 bpm | ≤ 50 mmHg | ≤ 90 mmHg |
| Grade 1 or mild | - | > 90 mmHg - < 100 mmHg | > 140 mmHg - < 160 mmHg |
| Grade 2 or moderate | - | ≥100 mmHg - < 110 mmHg | ≥160 mmHg - < 180 mmHg |
| Grade 3 or severe | - | ≥ 110 mmHg | ≥ 180 mmHg |
| Abnormally high | ≥ 120 bpm | - | - |

* The classification of AEs related to hypotension and hypertension will be done according to the WHO grading scale

| Abnormality Code | Vital Signs parameter | |
|---|---|--|
| | Temperature (°C/°F) | Respiratory rate (breaths per minute) |
| Grade 1 or mild | > 38.0 - <= 38.6 °C or > 100.4 - <= 101.5 °F | 17-20 |
| Grade 2 or moderate | > 38.6 - <= 39.3 °C or > 101.5 - <= 102.7 °F | 21-25 |
| Grade 3 or severe | > 39.3 - <= 40.0 °C or > 102.7 - <= 104.0 °F | >25 |
| Grade 4 or potentially life-threatening | >40.0°C or > 104.0°F | |

ATTACHMENT 2. ECG ABNORMALITIES

The following abnormalities are defined for ECG:

| Abnormality Code | ECG parameter | | | |
|--|---------------|----------|----------|-------------------------|
| | HR | PR | QRS | QT _{corrected} |
| Abnormalities on actual values | | | | |
| Abnormally low | < 45 bpm | < 110 ms | - | - |
| Abnormally high | ≥ 120 bpm | > 220 ms | ≥ 120 ms | - |
| Borderline prolonged QT (males) | - | - | - | 450 ms < QTc ≤ 480 ms |
| Borderline prolonged QT (females) | - | - | - | 470 ms < QTc ≤ 480 ms |
| Prolonged QT | - | - | - | 480 ms < QTc ≤ 500 ms |
| Pathologically prolonged QT | - | - | - | QTc > 500 ms |
| Abnormalities on changes from baseline (ΔQTc) | | | | |
| Normal QTc change | - | - | - | ΔQTc < 30 ms |
| Borderline QTc change | - | - | - | 30 ms ≤ ΔQTc ≤ 60 ms |
| Abnormally high QTc change | - | - | - | ΔQTc > 60 ms |

ATTACHMENT 3. CRS DERIVATION

The CRS categories should be evaluated from 6 to 1. First check if the subject falls in category 6 (has the subject died?) if not then we evaluate category 5, if not 5 then evaluate category 4 and so on.

The CRS is evaluated at baseline and per day, relative to the start of the study drug intake. The baseline CRS is based on the data obtained at the time of randomization.

Notes:

- The CRS scores will be calculated up to day 28 for subjects who are still in the trial at day 28. Participants who die before they discontinued the trial before day 28 will be considered to continue the trial up to and including day 28.
- If the subject has different types of oxygen supplementation on a single day, the worst type will be considered to derive the score.
- In case the subject withdrew from the study for other reason than death, the CRS will not be calculated from the next day onwards. A record indicating this type of missing scores should be foreseen in the ADAM data sets.
- Intermittent missing values can occur (eg. Due to incomplete supplementary oxygen information). For intermittent missing values, a record should be foreseen in the adam dataset. It should be possible to make the distinction between this type of missing values and the missing values due to trial discontinuation.

Hospitalized and Not Hospitalized

Rules will be applied in the order as described below. The first rule fulfilled by a subject will be considered.

1. If a subject is discharged to the alternate care settings “2. Different hospital”, “3. Acute Care Facility”, “4. Subacute care facility” or “7. Hospice/Palliative Discharge”, the subject will be considered hospitalized until day 28 or until trial discontinuation. The subject will be categorized in the category the subject was in at the moment of discharge.
2. If a subject is discharged ‘against medical advice’, the subject will be considered hospitalized on the day of discharge and on the day after discharge (unless the subject discontinued the trial). The subject will be categorized in the category the subject was in at the moment of discharge. The CRS will be considered missing on subsequent days.
3. If a subject is hospitalized, but is ‘ready for discharge’ according to the investigator, the subject will be considered hospitalized up to and including the first day on which the subject was considered ready for discharge. The subject will be considered “Not hospitalized” from the day after until day 28/trial discharge (unless the status changes back to “not ready for discharge”).
4. If a subject is discharged, but is ‘not ready for discharge’ according to the investigator, the subject will be considered hospitalized up and including 1 day after the day of discharge or until trial discontinuation. The subject will be categorized in the category the subject was in at the moment of discharge. The subject will be considered non hospitalized from 2 days after the day of discharge onwards until day 28/trial discontinuation.
5. If a subject is discharged from the hospital, the day of discharge will be considered as “hospitalized”. The subject will be categorized in the category the subject was in at the moment of discharge. After this day, the subject will be considered “Not hospitalized” until day 28/trial discontinuation.

CRS Derivation

The Ordinal Clinical Recovery Scale can be derived from Baseline up to and including Day 28, or until trial discontinuation. Participant who died before day 28 (before or after hospital discharge, but before trial discontinuation) will be considered to continue the trial up to and including day 28.

For the derivation, we will start with the highest score.

If the subject didn't fall into this category, we will check for the next highest score.

- **Score 6:** Based on the status of the participant on the day of the assessment (based on the date of death).

Based on Type of Oxygen Supplementation page:

- **Score 5:** At least one of the following scores is ticked:
 - IMV
 - Extra Corporeal Membrane Oxygenation
 - The question “Is the subject on Mechanical Ventilation” is answered “No”, and the question “From a Medical Perspective, should the patient be on IMV?” is answered “Yes”. (on Subject Status Form)*
- * To comply with the note: “*If a participant declines medically-indicated mechanical ventilation, the participant will be categorized according to the care they would otherwise have received on that day*”
- **Score 4:**
 - Subject is on supplemental oxygen and the FiO2 is $\geq 50\%$.
- **Score 3:**
 - Hospitalized & **requiring low flow supplemental oxygen, defined as**
 - Receiving supplemental oxygen (through a face mask, nasal cannula, high flow nasal canula or other where FiO2 is $< 50\%$) & the patient was not able to sustain a blood oxygen saturation of $> 93\%$ when breathing room air:
 - If assessed for blood oxygen saturation when breathing room air, SpO2 value should be $\leq 93\%$
 - If not assessed for blood oxygen saturation when breathing room air (for any reason), SpO2 value is assumed to be ≤ 93
 - OR
 - Not on supplemental oxygen and the minimum of all measured SpO2 values during the day $\leq 93\%$ (as this will be measured at least 4 times/day)
- **Score 2:**
 - Hospitalized according to hospitalization rules as discussed earlier.
- **Score 1:**
 - Not hospitalized, including subjects on low level of oxygen.

A distinction will be made between subjects discharged and in need of (score 1.2) or not in need of (score 1.1) oxygen supplementation as indicated by the investigator on the discharge questionnaire. This distinction will not be made when calculating improvements on the CRS, for which score 1 will be used in both cases.

Some examples

Case 1: Discharged from hospital on Day 6 (Rule 5)

| Case 1 | Day 3 | Day 4 | Day 5 | Day 6 | Day 7 | Day 8 to Day 28 |
|-------------------------|--------------|--------------|--------------|------------|-------|-----------------|
| Against medical advice? | | | | --/No | | |
| Status (SS*) | hospitalized | hospitalized | hospitalized | Discharged | | |
| Discharged to** | | | | 1/5/.. | | |
| ready (SS*) | --/Not ready | --/Not ready | --/Not ready | --/Ready | | |
| CRS | >1 | >1 | >1 | >1 | 1 | 1 |

Case 2: Alternate care setting (rule 1): hospitalized until Day 28

| Case 2 | Day 3 | Day 4 | Day 5 | Day 6 | Day 7 | Day 8 to Day 28 |
|-------------------------|--------------|--------------|--------------|------------------------|-------|-----------------|
| Against medical advice? | | | | --/No/YES | | |
| Status (SS*) | Hospitalized | hospitalized | hospitalized | Discharged | | |
| Discharged to** | | | | 2/3/.. | | |
| ready (SS*) | --/Not ready | --/Not ready | --/Not ready | --/Ready/ Not ready | | |
| CRS | >1 | >1 | >1 | >1 | >1 | >1 |

Case 3: Against medical advice (rule 2): hospitalized on Day 6 and 7, missing thereafter

| Case 3 | Day 3 | Day 4 | Day 5 | Day 6 | Day 7 | Day 8 to Day 28 |
|-------------------------|--------------|--------------|--------------|------------------------|-------|-----------------|
| Against medical advice? | | | | YES | | |
| Status (SS*) | hospitalized | hospitalized | hospitalized | Discharged | | |
| Discharge to** | | | | 1/5/.. | | |
| ready (SS*) | --/Not ready | --/Not ready | --/Not ready | --/Ready/ Not ready | | |
| CRS | >1 | >1 | >1 | >1 | >1 | Missing |

*SS = Subject Status

1= not hospitalized; > 1 = hospitalized

** 1=Patient's Home; 2=Different Hospital; 3=Acute Care Facility; 4=Subacute care facility

5=Long-Term Facility; 6=Rehab Facility; 7=Hospice/Palliative Discharge; 8=Other

Case 4: Ready for discharge at Day 5 (rule 3)

| Case 4 | Day 3 | Day 4 | Day 5 | Day 6 | Day 7 | Day 8 to Day 28 |
|----------------------------|--------------|--------------|--------------|--------------|------------|-----------------|
| Against medical advice? | | | | | --/NO | |
| Status (SS*) | hospitalized | hospitalized | hospitalized | hospitalized | Discharged | |
| Discharge to** ready (SS*) | --/Not ready | --/Not ready | Ready | --/Ready | 1/5/.. | |
| CRS | >1 | >1 | >1 | 1 | --/Ready | 1 |

Case 5: Discharged from hospital on Day 6, but not ready for discharge (Rule 4)

| Case 5 | Day 3 | Day 4 | Day 5 | Day 6 | Day 7 | Day 8 to Day 28 |
|-----------------------------|--------------|--------------|--------------|------------|--------|-----------------|
| Against medical advice? | | | | --/NO | | |
| Status (SS*) | hospitalized | hospitalized | hospitalized | Discharged | | |
| Discharged to** ready (SS*) | --/Not ready | --/Not ready | --/Not ready | Not ready | 1/5/.. | |
| CRS | >1 | >1 | >1 | >1 | >1 | 1 |

Case 6: Ready for discharge at Day 5, Not ready for discharge at Day 6 (rule 3)**Discharged from hospital on Day 7 (Rule 5)**

| Case 6 | Day 3 | Day 4 | Day 5 | Day 6 | Day 7 | Day 8 to Day 28 |
|----------------------------|--------------|--------------|--------------|--------------|------------|-----------------|
| Against medical advice? | | | | --/NO | | |
| Status (SS*) | hospitalized | hospitalized | hospitalized | hospitalized | Discharged | |
| Discharge to** ready (SS*) | --/Not ready | --/Not ready | Ready | Not ready | 1/5/.. | |
| CRS | >1 | >1 | >1 | >1 | >1 | 1 |

*SS = Subject Status

1= not hospitalized; > 1 = hospitalized

** 1=Patient's Home; 2=Different Hospital; 3=Acute Care Facility; 4=Subacute care facility

5=Long-Term Facility; 6=Rehab Facility; 7=Hospice/Palliative Discharge; 8=Other

Case 7: Ready for discharge at Day 4, Not ready for discharge at Day 5 (rule 3)
Discharged from hospital on Day 6, but not ready for discharge (Rule 4)

| Case 7 | Day 3 | Day 4 | Day 5 | Day 6 | Day 7 | Day 8 to Day 28 |
|----------------------------|--------------|--------------|--------------|-------------------|-------|-----------------|
| Against medical advice? | | | | —/NO | | |
| Status (SS*) | hospitalized | hospitalized | hospitalized | Discharged 1/5/.. | | |
| Discharge to** ready (SS*) | --/Not ready | Ready | Not ready | Not ready | | |
| CRS | >1 | >1 | >1 | >1 | >1 | 1 |

Case 8: Ready for discharge at Day 4, Not ready after ready at Day 6 (Rule 3)
Discharged from hospital on Day 6, but not ready (Rule 4)

| Case 8 | Day 3 | Day 4 | Day 5 | Day 6 | Day 7 | Day 8 to Day 28 |
|----------------------------|--------------|--------------|--------------|-------------------|-------|-----------------|
| Against medical advice? | | | | —/NO | | |
| Status (SS*) | hospitalized | hospitalized | hospitalized | Discharged 1/5/.. | | |
| Discharge to** ready (SS*) | Not ready | Ready | --/Ready | Not ready | | |
| CRS | >1 | >1 | 1 | >1 | >1 | 1 |

Case 9: Ready for discharge at Day 5 (rule 3)

| Case 9 | Day 3 | Day 4 | Day 5 | Day 6 | Day 7 | Day 8 to Day 28 |
|----------------------------|--------------|--------------|--------------|--------------|-------------------|-----------------|
| Against medical advice? | | | | | —/NO | |
| Status (SS*) | hospitalized | hospitalized | hospitalized | hospitalized | Discharged 1/5/.. | |
| Discharge to** ready (SS*) | --/Not ready | --/Not ready | Ready | -- | --/Ready | |
| CRS | >1 | >1 | >1 | 1 | 1 | 1 |

*SS = Subject Status

1= not hospitalized; > 1 = hospitalized

** 1=Patient's Home; 2=Different Hospital; 3=Acute Care Facility; 4=Subacute care facility

5=Long-Term Facility; 6=Rehab Facility; 7=Hospice/Palliative Discharge; 8=Other

Case 10: Rule 3 (ready at day 6)

| Case 10 | Day 3 | Day 4 | Day 5 | Day 6 | Day 7 | Day 8 to Day 28 |
|----------------------------|--------------|--------------|--------------|--------------|------------|-----------------|
| Against medical advice? | | | | | --/NO | |
| Status (SS*) | hospitalized | hospitalized | hospitalized | hospitalized | Discharged | |
| Discharge to** ready (SS*) | Not ready | Not ready | Not ready | Ready | 1/5/.. | |
| CRS | >1 | >1 | >1 | >1 | --/Ready | 1 |

Case 11: Not ready after ready (Rule 3)**Discharged while not ready on Day 6 (Rule 4)**

| Case 11 | Day 3 | Day 4 | Day 5 | Day 6 | Day 7 | Day 8 to Day 28 |
|----------------------------|--------------|--------------|--------------|------------|-------|-----------------|
| Against medical advice? | | | | --/NO | | |
| Status (SS*) | hospitalized | hospitalized | hospitalized | Discharged | | |
| Discharge to** ready (SS*) | Not ready | Not ready | Ready | 1/5/.. | | |
| CRS | >1 | >1 | >1 | >1 | >1 | 1 |

Case 12: Ready for discharge at Day 5 (rule 3)**Alternate care setting (rule 1): hospitalized until Day 28**

| Case 12 | Day 3 | Day 4 | Day 5 | Day 6 | Day 7 | Day 8 to Day 28 |
|----------------------------|--------------|--------------|--------------|------------|-------|-----------------|
| Against medical advice? | | | | --/NO | | |
| Status (SS*) | hospitalized | hospitalized | Hospitalized | Discharged | | |
| Discharge to** ready (SS*) | --/Not ready | Ready | -- | 2/3/.. | | |
| CRS | >1 | >1 | 1 | >1 | >1 | >1 |

*SS = Subject Status

1= not hospitalized; > 1 = hospitalized

** 1=Patient's Home; 2=Different Hospital; 3=Acute Care Facility; 4=Subacute care facility

5=Long-Term Facility; 6=Rehab Facility; 7=Hospice/Palliative Discharge; 8=Other

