 - General safety chemistry: total protein, albumin, aspartate aminotransferase (AST), alanine aminotransferase (ALT), alkaline phosphatase (ALP), total bilirubin, glucose, sodium, potassium, calcium, phosphate, magnesium, chloride, bicarbonate, creatinine, blood urea nitrogen (BUN), creatine phosphokinase (CPK), lactate dehydrogenase (LDH), lactate, and troponin. If ALT or AST >3x ULN or 3x the entry level (if entry levels were >ULN), also provide conjugated bilirubin (direct), unconjugated bilirubin (indirect).
- m. Culture results (bacterial, fungal, or viral) including site of infection and specimen source (bronchoalveolar lavage [BAL], tracheal aspirate, sputum, blood, urine, etc.), performed as part of patients' workup for new infections, should be reported. Analyses will be performed by the local laboratory.
- n. For participants discharged or who discontinued the study prior to Day 28 and did not withdraw consent, phone calls will be conducted on Day 28 and during the post Day 28 Follow-up Phase to record concomitant medication, the vital status, the occurrence of AEs, self-reported oxygen need, self-reported pregnancy status and the history of readmission since last contact.
- o. Whenever possible, vital status will be recorded if the patient is alive. If the participant is deceased, date and cause of mortality should be recorded in the eCRF. Death should be documented as SAE.
- p. NP swabs will be used to collect secretions from participants to explore quantification of viral load of SARS-CoV-2. For each participant, NP sampling should be done at approximately the same time (± 4 hours) on each sampling day and from the same nostril.
- q. If an NP sample for detection of SARS-CoV-2 (local SOC) will be collected on the same day as the NP sample for quantification of SARS-CoV-2 (central lab), only one NP sample should be collected. The sample should be aliquoted and the remaining aliquots of the NP samples should be stored and sent to the central lab for quantification of SARS-CoV-2.
- r. SARS-CoV-2 positivity should be documented based on local testing on any specimen, by RT-PCR, any time before randomization. This might require a local test using an NP swab obtained at screening.
- s. After randomization, SARS-CoV-2 positivity will be confirmed in a central lab by quantitative RT-PCR. The baseline sample needs to be collected predose, as close as possible to dosing.

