5.2 Primary Efficacy Endpoint(s)

5.2.1 Definitions

Six-point ordinal clinical recovery scale

The 6-point ordinal clinical recovery scale (CRS) provides 6 mutually exclusive conditions ordered from best to worst, and the score reflects the participant's worst situation on the day of the assessment:

1. Not hospitalized
2. Hospitalized, not requiring supplemental oxygen
3. Hospitalized, requiring low flow supplemental oxygen
4. Hospitalized, on non-invasive ventilation, nonrebreather mask or high flow oxygen device
5. Hospitalized, on IMV or ECMO
6. Death

The CRS can be derived from baseline up to and including day 28. The CRS will be missing after trial discontinuation if the participant discontinued the trial for other reason than death. Participants who die before day 28 (before or after discharge from hospital) will be considered to continue the trial up to and including day 28.

The CRS categories are defined below. For ease of categorization, the categories are defined from worst to best. A participant will be evaluated in the same ordering of the categories as below. Once a participant fulfils the criteria for a category, the category is assigned to the participant and the evaluation stops.

6. Death
 - o Participant died at any time on the day of assessment or earlier (all-cause mortality).
5. Hospitalized, on IMV or ECMO

- o IMV or ECMO is used at any time on the day of assessment, OR
- o From a Medical Perspective, the participant should have been on IMV on the day of the assessment

4. Hospitalized, on non-invasive ventilation, nonrebreather mask, or high flow oxygen device
 - o The participant is on supplemental oxygen and the worst FiO₂ is $\geq 50\%$.
3. Hospitalized, requiring low flow supplemental oxygen
 - o On supplemental oxygen with worst FiO₂ $< 50\%$ and the participant was not able to sustain a blood oxygen saturation of $> 93\%$ when breathing room air, OR
 - o Not on supplemental oxygen and the minimum of all available SpO₂ values during the day is $\leq 93\%$
2. Hospitalization, not requiring supplemental oxygen
 - o Hospitalized according to the status described below
1. Not hospitalized, including subjects on low level of oxygen

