5.2.3 Analysis Methods

All participants for which the trial is still ongoing at Day 28 and without sustained clinical improvement by Day 28 will be censored on Day 28. Participants that discontinue the study before day 28 will be censored at the last assessment of the CRS, unless they had an event of sustained clinical improvement prior to discontinuation. Participants that died at day 28 or earlier will be censored at day 28, irrespective of whether a clinical improvement occurred prior to death.

The primary hypothesis of this study is that Sirukumab in combination with SOC results in a statistically significant shorter time to sustained improvement (defined as an improvement of at least 2 categories relative to baseline on the 6-point ordinal CRS) versus placebo in combination with SOC, in participants with confirmed critical COVID-19.

The primary hypothesis will be evaluated based on the Logrank test, stratified for the stratification factors (age [<65 and ≥ 65 years] and use of IMV [yes/no]). This test will be performed 2-sided at a 5% significance level. The actual values of the stratification factors will be used, not as randomized.

The hazard ratio of sustained clinical improvement for experimental treatment versus placebo, from baseline until day 28 will be considered as the population-level summary measure of the treatment effect for the primary estimand. The hazard ratio will be estimated in a Cox proportional hazards model stratified for the stratification factors and with treatment as a single covariate. A value larger than 1 indicates the chance of improvement is larger in the experimental treatment group. The 95% Wald confidence interval will be added.

The Log-rank test might generate a different p-value compared to that of the Wald test of the hazard ratio. The Logrank test will be used for formal inference (and not the Wald p-value or CI from the hazard ratio).

Cumulative proportion of patients with clinical improvement, by treatment, will be provided using the complement of the Kaplan Meier curve. The analyses will be completed with the median time to clinical improvement (if reached) and the proportion of participants who had their clinical improvement on day 7, 14, 21 and 28; all per Kaplan Meier method. The complementary log-log transform method is used to calculate the 95% confidence intervals.

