5.3 Key Secondary Endpoints

5.3.1 Definitions

Similar as for the primary endpoint, the definitions as specified in section [5.2.1](#) will be used for the key secondary endpoints.

Clinical improvement at Day 28

Clinical Improvement is obtained if the score on the CRS improved with at least 2 categories at Day 28 with respect to the baseline score.

All-cause mortality up to Day 28

All-cause mortality is defined as score 6 on the CRS at Day 28.

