- Participants whose last score on the CRS was equal to 1 and that were not reported as having died before or at day 28 will be analyzed according to the composite strategy and they will be considered as alive (Death at Day 28=no).

Population level summary measure:

The difference in proportion of participants with ‘Death by day 28’ for experimental treatment versus placebo.

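### SAP Attachment 3 carries a death to Day 28 as score 6 only if it precedes trial discontinuation, which conflicts with the death rules in SAP 5.2.3 and 5.3.2

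*SAP*

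**What the plan says.** Attachment 3 states its limit twice. Under CRS Derivation: "Participant who died before day 28 (before or after hospital discharge, but before trial discontinuation) will be considered to continue the trial". In the notes: "Participants who die before they discontinued the trial before day 28 will be considered to continue the trial up to and including day 28". The notes also stop the scale after other withdrawals: "In case the subject withdrew from the study for other reason than death, the CRS will not be calculated from the next day onwards".

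SAP 5.2.1 has the same carry-forward without the limit: "Participants who die before day 28 (before or after discharge from hospital) will be considered to continue the trial". The sentence just before it, however, sets the CRS to missing after a discontinuation for any reason other than death.

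SAP 5.2.3 is unconditional for the primary endpoint: "Participants that died at day 28 or earlier will be censored at day 28, irrespective of whether a clinical improvement occurred prior to death". SAP 5.3.2 treats any death by Day 28 as a failure for the Day 28 improvement endpoint in the same way.

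For mortality, SAP 5.3.1 says: "All-cause mortality is defined as score 6 on the CRS at Day 28". SAP 5.3.2 then gives two rules. Discontinuation with a score above 1 counts as death. Being counted alive is reserved for: "Participants whose last score on the CRS was equal to 1 and that were not reported as having died before or at day 28".

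Deaths after discontinuation can come to light. Footnote n of the protocol's Schedule of Activities says: "For participants discharged or who discontinued the study prior to Day 28 and did not withdraw consent, phone calls will be conducted on Day 28". Vital status is among the items recorded on that call.

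**The concern.** Attachment 3 is the text a programmer would build the daily scores from, and all three confirmatory endpoints draw on those scores. Its limit on deaths is absent from the analysis rules, and nothing in the SAP says which text prevails. The discontinuation rules pull the other way from the death rules. Sustained improvement (5.2.1) is checked for loss only until discontinuation. Both 5.2.3 and 5.3.2 keep an improvement reached before discontinuation as an event or a success.

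A documented death by Day 28 could therefore be classified in opposite ways in the primary endpoint and in the Day 28 improvement endpoint. In one narrow case it would have no stated mortality outcome. If the conflict is noticed only after unblinding, whichever reading is chosen is open to criticism.

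**Working it through.** The point disputes no stated figure, so the check is a comparison of texts. One figure is still relevant. SAP 1.4 claims at least 80% power for the log-rank test with 74 and 37 participants. It assumes log-normal times in survivors (medians 16.8 and 28 days, SD 0.9), mortality of 20% and 40%, and every death censored at Day 28. An unstratified simulation of 4,000 trials on those inputs gives 0.81 with times in whole days and 0.82 with continuous times. The expected control improvement rate also reproduces: 0.60 × 0.50 = 0.30. The design calculation thus uses the 5.2.3 death rule, and adopting that rule throughout changes no design figure.

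Now take one participant through the texts. Before Day 12 the participant improves by at least two categories. The participant discontinues on Day 12 without withdrawing consent, and the Day 28 call records a death on Day 20.

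1. *Daily scores.* Under Attachment 3 the death came after discontinuation, so there is no carry-forward and the CRS is missing from Day 13. No score 6 exists.
2. *Primary endpoint.* No loss of improvement was documented up to discontinuation, so the improvement counts as sustained, and the 5.2.3 discontinuation sentence keeps the event. The next sentence of 5.2.3, on deaths, censors the same participant at Day 28.
3. *Day 28 improvement.* The discontinuation bullet in 5.3.2 gives success; the death bullet gives failure.
4. *Mortality, last score above 1.* 5.3.2 counts the participant as dead because of the score at discontinuation. The death is not lost.
5. *Mortality, last score 1.* The score-above-1 rule does not apply. The alive rule does not apply either, because a death was reported. 5.3.1 asks for a score 6 that was never assigned.

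| Endpoint | Attachment 3 with discontinuation rules | Death rules in 5.2.3 and 5.3.2 |
|---|---|---|
| Time to sustained improvement | Event | Censored at Day 28 |
| Day 28 improvement | Success | Failure |
| Death by Day 28, last score above 1 | Yes | Yes |
| Death by Day 28, last score 1 | No score 6 | Not alive, but no explicit line |

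*Who can be in this position?* Protocol 7.2 lists three reasons for withdrawal: loss to follow-up, withdrawal of consent, and death. Under 7.3 a lost participant found to have died is no longer treated as lost, and vital status is not collected after consent withdrawal. Only the group named in footnote n remains: discontinued, consent not withdrawn. The documents give no size for it.

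*Weight of one participant.* One death is 1/37 = 2.7 percentage points of control mortality or 1/74 = 1.4 points of sirukumab mortality. This is a unit of scale, not an estimate.

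**The case against.** The strongest reply is that Attachment 3 only derives daily scores, while events and censoring are set in 5.2.3 and 5.3.2. Those death rules do not depend on a score 6 having been assigned, so a programmer who applies them directly gets the intended result. The mortality estimand is itself worded as death by Day 28, and a reported death is deliberately kept out of the alive rule. Attachment 3 may also be read as spelling out 5.2.1, which already makes the CRS missing after a non-death discontinuation. Finally, protocol 7.2 and 7.3 leave almost nobody to whom the question applies.

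Much of this stands. The conflict with 5.2.1 is only partial. Misclassification is possible, not certain. The affected group is close to empty, although footnote n prevents ruling it out.

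The reply does not remove the conflict. 5.2.3 and 5.3.2 each place a death rule beside a discontinuation rule that gives the opposite answer for the same participant, without an order of precedence. 5.3.1 does define mortality by the score.

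**Conclusion.** Attachment 3 contradicts the death rules of SAP 5.2.3 and of the Day 28 improvement estimand in 5.3.2. If it is programmed together with the until-discontinuation wording, a documented death could stay a primary event. In mortality there is a gap only for a last score of 1 followed by a recorded death after discontinuation. This rests on at least one participant discontinuing before Day 28 with consent intact and being recorded dead by Day 28. Few can qualify, and no effect size can be derived.

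Three stronger readings are tempting, and the documents support none of them:

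- *Known deaths generally drop out of mortality.* Deaths after hospital discharge but before discontinuation are covered by Attachment 3 itself, and deaths after discontinuation with a last score above 1 are counted by 5.3.2.
- *Such deaths count in favour of the arm in which they occur.* That follows only if the 5.2.3 and 5.3.2 death rules are ignored.
- *One such death would change the mortality conclusion.* Counts can be chosen near the one-sided 5% line: 13/37 v 15/74 gives p = 0.045 (pooled z-test, unstratified). With one control death coded alive, 12/37 v 15/74 gives 0.080; with it coded missing, 12/36 v 15/74 gives 0.068. These counts are selected, not expected, and mortality is tested only if the two earlier tests succeed.

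**What to change.** Before database lock:

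- In Attachment 3, delete the qualifier about trial discontinuation from both death sentences (the last clause of the parenthesis under CRS Derivation, and the corresponding words in the notes).
- In 5.2.1 and Attachment 3, except documented deaths from the sentence that makes the CRS missing after a non-death discontinuation.
- State once that any death documented on or before Day 28 gives score 6 from the date of death through Day 28 and sets Death by Day 28 to yes, whatever the discontinuation date or last score.
- In 5.2.3 and 5.3.2, state that the death rule takes precedence over the discontinuation rule.

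Deaths after consent withdrawal, which protocol 7.3 does not collect, remain outside this rule. The cost is a few sentences in the SAP and a small change to the derivation. No new data are needed, and neither sample size nor power changes.
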